3.2 Primary Study Endpoints

Due to the pilot phase design of this clinical trial, it is not feasible to designate primary study endpoints. With this in mind, we do consider the biomechanical assessments and electrophysiology tests to be the primary sets of endpoints used to quantify TS and ES-related datasets associated with addressing the specific aims of this proposal.

3.3 Secondary Study Endpoints

Similarly, it is not feasible to designate secondary study endpoints. We do consider clinical assessments of spasticity and subjective surveys to be secondary study endpoints.

3.4 Primary Safety Endpoints

Primary safety endpoints of the study will be oriented to adverse events that could originate from the implantation of the ES electrodes, or the operation of either neurostimulator device as well as to those that could arise from performing the locomotor rehabilitation sessions. Patients will be asked to report any discomfort that they encounter throughout the study. A detailed selection of the candidates by the Principal Investigators and the study team will be crucial to select individuals who fit the inclusion criteria of the study, minimizing risk for potential adverse events throughout the study. Subjects will undergo a screening phase oriented to identify conditions that could potentially represent a higher than the expected risk for conducting this study.

To visualize electrode positioning of the ES neurostimulator system, fluoroscopy and spine computed tomography will be performed. To limit adverse events that could result from operating the neurostimulator device, stimulation parameters will be selected within safe ranges as provided by the manufacturer's specifications of ES pulse generators. Specifically, we will deliver stimulation within the following ranges:

ES parameters: pulse width 50-1000 microseconds; frequency 0.5-200 Hz; amplitude 0-25.5 mA

The procedure to connect the externalized ends of the percutaneous electrodes (model 3086) to the Ripple NOMAD will consist of minimizing strain on the connections by creating loops in the externalized lead wires and lead extensions (model 3386). The loops will be positioned in proximity to the implant site using adhesive tape. Additionally, each connection will be secured using adhesive tape. Finally, each connection and implantation site, as well as the strain relief loops, will be protected using an adhesive bandage.

During sessions of rehabilitation with stimulation, the looped lead wires and lead extensions will be connected to Abbott's battery-powered pulse generator (model 3599) via "multilead trial cables" (model 3013). Stimulation waveforms and electrode configurations will be transmitted wirelessly from the "clinician programmer" (model 3874) to the battery powered pulse generator. The battery-powered pulse generator, multilead trial cables, and clinician programmer are manufactured by Abbott for use with their ES system.

4 SUBJECT, SELECTION, ENROLLMENT, AND WITHDRAWAL

A total of eight humans with a history of a traumatic SCI will be enrolled in this pilot phase clinical trial (**Table 2**). **Four** subjects will be assigned to "intervention 1" cohort and **four** will be assigned to the "intervention 2" cohort. Subjects will be selected based on the criteria described within sections 4.1 and 4.2:

[figure not shown]

Table 2: Study Timeline

4.1 Inclusion Criteria

- Spinal cord injury due to trauma located at or above the tenth thoracic vertebrae (T10)
- American Spinal Injury Association grading scale of A-D (2 from each) below the level of SCI
- Intact spinal reflexes below the level of SCI
- At least 1-year post-SCI
- At least 22 years of age
- Willing to use medically acceptable methods of contraception, if female and of childbearing potential

4.2 Exclusion Criteria

- Currently a prison inmate, or awaiting trial, related to criminal activity
- Pregnancy at the time of enrollment
- History of chronic and/or treatment resistant urinary tract infection
- Unhealed decubitus ulcer
- Unhealed skeletal fracture

- Untreated clinical diagnosis of depression
- Undergoing, or planning to undergo, diathermy treatment
- Active participation in another interventional clinical trial
- Presence of conditions or disorders which require MRI monitoring
- Other implanted stimulation devices (e.g. deep brain stimulator, cardiac pacemaker, diaphragmatic pacer, etc.)
- A history of coagulopathy or other significant cardiac or medical risk factors for surgery
- Current use of a ventilator
- Clinically diagnosed cardiopulmonary complications such as chronic obstructive pulmonary disease, cardiac failure, or heart arrhythmia that contraindicate changes in body position such as supine-to-sit-to-stand activities, prolonged standing, or stepping
- History of frequent hypotension characterized by light headedness, or loss of consciousness
- History of frequent hypertension characterized by headache, or bradycardia
- History of frequent, severe, autonomic dysreflexia
- Any illness or condition which, based on the research team's assessment, will compromise with the patient's ability to comply with the protocol, patient safety, or the validity of the data collected during this study.

4.3 Subject Recruitment, Enrollment and Screening

A total of 8 subjects will undergo the experiments described within this protocol. Subjects will be recruited from the following:

- Mayo Clinic's volunteer research subject database
- Mayo Clinic's clinical trials website
- Mayo Clinic's electronic medical record database search tools
- ClinicalTrials.gov

Prior to participating in the screening phase, a member of the research team will provide a detailed explanation of the study and answer questions asked by the potential study subject. If the potential subject is willing to participate in the study, they will be given sufficient time to make an informed decision, review relevant informed consent documents, and ask questions. Once questions and concerns have been addressed to the potential subject's satisfaction, the informed consent form will be signed and dated by the subject and an Investigator. A copy of the signed consent documents will be provided to the subject. The original signed consent documents will be retained within study records.

Following informed consent, screening tests will be performed including a thorough history and physical examination by a physician and physical therapist. Pre-existing clinical results to screening assessments may be accepted at the investigators' discretion if the testing was done within the timeframe specified for each test in the Study Procedures section. The ASIA Impairment Scale (AIS) examination will also be completed during screening to determine severity and classification of SCI. Urine tests will be completed to rule out an active urinary tract infection; if the testing is positive for a urinary tract infection, the subject will be

retested after two weeks' time for resolution. The subject will also be screened during a mock-up therapy session utilizing body weight supported harness system over the treadmill and trainer assistance to facilitate stand and step activities while monitoring blood pressure, tolerance, and range of motion. Due to an absence of standardized clinical practice guidelines that inform rehabilitation task safety decisions, if any concerns related to upright and load bearing activities exists, i.e. limited range of motion of load bearing joints, high spasticity, low blood pressure, osteoporosis (defined as a DEXA t-score of -3.5 or lower at the spine and hip), or high body weight, participants will receive motor training while seated and/or supine on a mat table, to avoid injury related to load-bearing activities. Based on screening results, a final decision on study participation will be made by the PI and study team. If any exclusionary screening results are transitory in nature, the subject may be re-screened at the discretion of the investigators. Screening tests will be repeated as indicated in the Study Procedures section.

4.4 Early Withdrawal of Subjects

Subjects will be informed that they have the right to withdraw from the study at any time. Similarly, the PI has the authority to withdraw the subject from the study at any time.

4.4.1 When and How to Withdraw Subjects

Factors that may lead to withdrawal:

- Study subject health concerns
- Protocol violation (e.g., non-compliance)
- Study-related serious adverse events
- Study subject's decision to pursue activities outside of the study protocol, that in the opinion of the PI, may compromise data collected within the study protocol
- The emergence of other problems, events, or information, that may adversely affect the rights, safety, or welfare of the study subject, or may substantially compromise data collected within the study protocol

If a serious adverse event occurs during an activity described in this protocol, a consensual decision will be made between the study subject and the PI regarding withdrawal from the study.

In the event of study withdrawal, the ES electrodes will be surgically explanted. If explanation surgery is urgent due to concern for the subject's health, the cost of the explanation surgery will be covered by the research study. Aside from standard surgical recovery, no adverse effects are anticipated from the removal of an epidural electrical stimulator.

If a subject is withdrawn from the study for any reason other than treatment-related adverse events, an additional subject may be recruited as a replacement within the same study cohort.

If a subject fails to attend protocol activities and fails to respond for follow-up, a communication attempt will be made to determine if non-compliance is related to an adverse event.

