1 INTRODUCTION

This document describes the protocol of a pilot stage clinical trial intended to study 8 humans diagnosed with chronic, incomplete, or complete loss of motor function below the level of traumatic spinal cord injury (SCI). The purpose of this trial is to improve the scientific understanding of how two electrical stimulation techniques, one which delivers electricity to the skin surface over the spine (transcutaneous spinal stimulation (TS)) and another which implants temporary percutaneous electrodes into the epidural space of the spinal cord (epidural spinal stimulation (ES)), facilitate spinal circuitry to enable function for individuals with SCI representing all levels of severity. Furthermore, we hope to determine responders versus non responders to spinal stimulation task-specific motor training following a condensed rehabilitation program as well as identify retained effects following 4 months of no intervention. Over the past decade, clinical investigations using either TS or ES have reported positive outcomes, such as regained control of leg movement (Gerasimenko, Lu, et al. 2015; P. S. H. PhD et al. 2011; Angeli et al. 2014; P. J. G. PhD et al. 2017; Gad et al. 2017) and cardiovascular improvements (Phillips et al. 2018; Harkema, Ditterline, et al. 2018; West et al. 2018). Independent investigations of either TS or ES have yielded some knowledge of the interactions between the electric field and spinal cord networks (Minassian, Persy, Rattay, Pinter, et al. 2007; Minassian, Persy, Rattay, Dimitrijevic, et al. 2007; Danner et al. 2016; Hofstoetter et al. 2018; Sayenko, Atkinson, Floyd, et al. 2015; Sayenko et al. 2014; Sayenko, Atkinson, Dy, et al. 2015; Rattay et al. 2000; Danner et al. 2013; Capogrosso et al. 2013).

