This study will include adult humans that sustained a traumatic SCI at least one year before trial enrollment. To qualify for this study, SCI severity must be previously diagnosed with an AIS classified injury. One participant will be enrolled from each AIS classification (A, B, C, and D) for each intervention. All injuries must be located at or above the tenth thoracic vertebrae. Detailed inclusion and exclusion criteria are provided within the appropriate section of this protocol.

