5.7 Masking/Blinding of Study

This is an unblinded study. The PIs, co-investigators, and subjects will know what treatment they received.

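### Replacement is matched on arm but not on AIS grade, and the completers-only analysis set lets subjects who received stimulation drop out of the results

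*Combined protocol and SAP*

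**What the plan says.** **Replacement.** Section 4.4.1 opens the rule with "If a subject is withdrawn from the study for any reason other than treatment-related adverse events" and continues that "an additional subject may be recruited as a replacement within the same study cohort". It is optional, and the cohort is its only matching condition. Section 4 uses the word cohort for the two intervention groups of four. No AIS grade, deadline, cap or decision-maker is given.

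**Grade quotas.** Section 1.1 says "One participant will be enrolled from each AIS classification (A, B, C, and D) for each intervention". Section 4.1 lists, as an inclusion criterion, "American Spinal Injury Association grading scale of A-D (2 from each) below the level of SCI". Neither refers to replacement or says whether a withdrawn subject still fills a place. Section 8.1 sets eight subjects and allows for contingency subjects without saying how they are chosen.

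**Allocation and withdrawal.** Section 5.2 fills the arms by availability or by the subject's own choice. Under Section 4.4, "the PI has the authority to withdraw the subject from the study at any time". The grounds in Section 4.4.1 include health concerns, non-compliance and new information that "may substantially compromise data collected within the study protocol". Lack of response is not among them. Section 4.4.2 requires the reason for withdrawal to be documented. Section 5.7 states: "The PIs, co-investigators, and subjects will know what treatment they received".

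**Analysis set and aims.** Section 8.3 defines one population, subjects who finished everything including follow-up, and lets the PI add someone who finished most of it. The Introduction says "we hope to determine responders versus non responders to spinal stimulation", and Section 1.4.1 wants the results to help identify candidates for ES.

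**The concern.** There are two separate problems.

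First, with no randomisation and four subjects per arm, the AIS quota is the only thing that makes the TS and ES groups alike in severity. A replacement rule that names the arm but not the grade can undo that balance. It can also change how many subjects supply some outcomes, because Section 6.6.1 (Overground mobility) assigns the TUG, BBS and 6MWT to subjects with motor incomplete injuries.

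Second, withdrawal can occur at any time up to the last follow-up at week 20, when the unblinded team has already seen how the subject performed under stimulation. Someone withdrawn then can be replaced and, under Section 8.3, disappears from the analysis. If leaving is related to poor response, even indirectly, both the TS-ES comparison and any account of who responds will look better than the experience of everyone who started stimulation.

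**Working it through.** **1. The plan's own count.** 4 grades x 1 subject x 2 arms = 8; 4 + 4 = 8; 2 per grade x 4 grades = 8. The figures agree for the first eight subjects.

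**2. After one withdrawal.** Seven remain: three grades with 2 subjects and one with 1 (3 x 2 + 1 = 7). What may be recruited depends on the reading:

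| Reading | Permitted replacement |
|---|---|
| Quotas apply to the subjects still in the study | Only the missing grade (4.1), in the vacated arm (1.1) |
| Withdrawn subject still counts towards the quota | None; every grade already has 2 |
| Section 4.4.1 taken alone | Any of the four grades, in the same arm |

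The first reading fits best with the contingency subjects in Section 8.1, but no text selects it.

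**3. Effect of matching on arm only.** Let s be the share of available candidates who have the lost grade (not in the documents; assumed). The chance that the replacement changes the grade mix is 1 - s: 90%, 75%, 60% and 50% for s = 10%, 25%, 40% and 50%. If arm and grade must both match, it is 0.

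For the mobility tests, assume that A and B are motor complete and C and D motor incomplete; the protocol does not spell this out. Each arm then has 2 of 4 contributors. A C or D subject replacing an A or B makes it 3 of 4, and the reverse makes it 1 of 4.

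**4. Effect on an apparent response rate.** The documents give no response rate and no withdrawal rate. Assume a true rate p, and that each non-responder is withdrawn with probability w while responders stay.

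- Dropped, not replaced: p / [p + (1 - p)(1 - w)].
  - p = 0.50, w = 0.20: 0.50 / (0.50 + 0.40) = 0.556.
  - p = 0.25, w = 0.30: 0.25 / (0.25 + 0.525) = 0.323.
- Dropped and replaced once, the replacement completing: p + (1 - p)wp.
  - p = 0.50, w = 0.20: 0.50 + 0.05 = 0.550.
  - p = 0.25, w = 0.30: 0.25 + 0.056 = 0.306.

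The excess is 0.05 to 0.07, or 0.4 to 0.6 of one subject in eight. Replacing once gives slightly less bias than not replacing, so the cause is withdrawal combined with the completers-only set.

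**5. Same check on a continuous outcome.** In simulated arms of four standard normal outcomes, the lowest value averages -1.03 SD. Always dropping that subject raises the arm mean by 1.03 / 3 = 0.34 SD; replacing that subject raises it by 1.03 / 4 = 0.26 SD. This is an extreme case, and Section 8.2 plans medians rather than means, but the ordering is the same.

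**6. Keeping everyone who started.** If withdrawn subjects stay in the denominator and their response status is known, the expected rate is [p + (1 - p)wp] / [1 + (1 - p)w]. This gives 0.55 / 1.10 = 0.50 and 0.306 / 1.225 = 0.25, so the true rates are recovered.

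**The case against.** The strongest defence is that the quotas already settle the grade. A replacement takes the vacated place, must meet the inclusion criteria like anyone else, and with seven remaining only the missing grade fits. That is the most natural reading, and it means that the first problem is a missing cross-reference. For the same reason, a reader might infer that no replacement can satisfy Sections 1.1, 4.1 and 4.4.1 together. The documents do not support that: it holds only if a withdrawn subject still occupies a quota place, and Section 8.1 foresees extra subjects.

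A reader might also infer that the plan provides for replacing non-responders. It does not. Non-response is not a listed ground, reasons are documented, treatment-related adverse events are outside the replacement rule, and Section 4.4.1 does not say that the PI decides on replacement. Nor does Section 8.2 plan a matched-pair analysis or a responder rate, and no responder is defined. Nor would an AIS-D subject replacing an AIS-A subject shift an arm mean on the 6MWT: on the usual grading an AIS-A subject would not take that test. What would change is the number of contributors.

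Finally, this is a pilot that designates no formal endpoints and has no power calculation. All of this stands and limits the size of the point. It does not answer the second problem: nothing makes withdrawal or replacement independent of outcomes, and the only defined analysis set drops the withdrawn subject unless the PI decides otherwise.

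**Conclusion.** The point holds in a limited form. Section 4.4.1 is not linked to the AIS quotas, so a site following it literally could change the severity mix of an arm. Separately, an open-ended withdrawal authority, an unblinded PI and a completers-only population allow subjects who received stimulation to leave the comparison and any responder description. This is a gap in safeguards. It is not evidence of intent, and replacement itself is not the source of the bias.

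Under the assumed inputs the responder rate rises by 5 to 7 percentage points. The size rests entirely on p and w, which the documents do not give, and on withdrawal falling only on non-responders. If withdrawal is unrelated to response, this bias is absent. With four subjects per arm and inexpensive wording available, the change is worth making.

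**What to change.** 1. **Section 4.4.1:** state that a replacement must be in the same arm and of the same AIS grade as the subject replaced, and that the quotas in Sections 1.1 and 4.1 apply to subjects who have not been replaced.
2. **Section 8.3:** report every subject who started stimulation, including any withdrawn and replaced, with the data collected, and keep them in any responder denominator. Make the completers set a supporting analysis. Section 8.2 already notes that mixed modelling does not need complete data.
3. **Section 4.4.2:** record the reason and date of withdrawal, and the decision to replace, before the replacement is screened.

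I would not bar replacement after the first outcome under stimulation. Table 3 places kinematics and EMG in training week 1, so an unrelated early dropout could then leave a grade-by-arm cell empty. Item 2 deals with the bias without that cost. A treatment-related adverse event can still leave a cell empty, since the replacement rule does not cover it; the report should show this.

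**Cost:** protocol wording only. A same-grade replacement may take longer to find, summaries will include some incomplete subjects, and the reported total will be eight plus any replaced subjects who had started stimulation.

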4.4.2 Data Collection and Follow-up for Withdrawn Subjects

If a subject withdraws or is withdrawn from the study for any reason before study completion, an attempt will be made to carry out an exit interview. The reason for withdrawal will be documented by the research team.

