5.2 Method for Assigning Subjects to Treatment Groups

Four subjects will be assigned to each treatment arm based on availability at the time the subject volunteers to participate (Total subjects studied: 8). If both arms are enrolling in

parallel at the time a subject volunteers to participate, he/she will be allowed to choose the treatment arm in which to enroll.

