In order to implant the temporary spinal electrodes, an incision will be made at the entry site to the depth of the subcutaneous fascia. Under fluoroscopy, an electrode insertion needle will be place into the epidural space using a paramedial approach until resistance is felt from the ligamentum flavum, followed by fluoroscopic visualization of the needle's position. Once positioning is confirmed, the needle stylet will be removed and the needle will be advanced into the epidural space.

Then, the leads are advanced in an anterograde fashion to deliver them into the intervertebral foramen under fluoroscopic guidance. Following electrophysiologic confirmation of electrode positioning, the needle and stylet will be removed, the implantation site will be dressed, and the leads will be secured to the skin via an adhesive bandage. The implantation site will be monitored for signs of infection, tissue erosion, or dislodged lead wires.

Procedure to explant ES electrode leads

After completing 12 sessions of rehabilitation with ES, the adhesive bandage covering the implantation site will be removed, the incision site will be opened, and the leads will be carefully retracted. Finally, the incision site will be cleaned and dressed.

If complications associated with temporary lead implantation (e.g., infection, severe lead migration, device malfunction, etc.) are observed, the PI will make an informed decision whether to perform explantation prior to completion of 12 rehabilitation sessions.

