8 STATISTICAL DESIGN AND POWER

8.1 Sample Size Determination

Due to the pilot phase of this clinical trial, no formal power calculations were performed for this study. The number of subjects was selected based on budgetary, space, and personnel time constraints. Eight subjects will be enrolled to complete the activities of this clinical trial, depending on need for contingency subjects. All subjects will receive either 1 month of TS and rehabilitation or 1 month of ES and rehabilitation. Following either intervention, all subjects will be followed for follow-up assessments at 2 time points during 4 additional months.

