9.5 Post-study AE

All unresolved AE will be followed by the PI until the AE is resolved, the participant is lost to follow-up, or the AE is otherwise explained. At the last scheduled visit, the PI will instruct each participant to report any subsequent event(s) that might reasonably be related to participation in this study. The PI will notify the institutional regulatory office of any death or AE that occurs at any time after participants have discontinued or terminated study participation and may reasonably be related to this study.

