10 DATA HANDLING AND RECORD KEEPING

10.1 Confidentiality

Participant information will be kept confidential and managed according to the requirements of the Health Insurance Portability and Accountability Act of 1996 (HIPAA). Those regulations require a signed subject authorization informing the subject of the following:

- What protected health information (PHI) will be collected from subjects in this study
- Who will have access to that information and why
- Who will use or disclose that information
- The rights of a research subject to revoke their authorization for use of their PHI

In the event that a participant revokes authorization to collect or use PHI, the PI, by regulation, retains the ability to use all information collected prior to the revocation of authorization. For participants that have revoked authorization to collect or use PHI, attempts will be made to obtain permission to collect at least vital status at the end of their scheduled study period.

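### Section 4.4.2 plans no scheduled outcome assessments after withdrawal, and the plan does not separate stopping stimulation from leaving the study

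*Combined protocol and SAP*

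**What the plan says.** The section of the combined protocol and SAP that governs data from withdrawn subjects, 4.4.2, contains two provisions. The first is that when someone leaves or "is withdrawn from the study for any reason before study completion, an attempt will be made to carry out an exit interview"; the second is that the cause is put on record. It names no outcome visit.

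Section 4.4.1 lists what may lead to withdrawal: health concerns, non-compliance, study-related serious adverse events, emerging problems or information, and the "Study subject's decision to pursue activities outside of the study protocol, that in the opinion of the PI, may compromise data collected". After a serious adverse event, the subject and the PI decide on withdrawal together. A withdrawn subject may be replaced in the same cohort, unless the reason was a treatment-related adverse event.

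Early removal of the leads is dealt with separately, in section 5.3. If complications such as infection, severe migration or malfunction are seen, "the PI will make an informed decision whether to perform explantation prior to completion of 12 rehabilitation sessions". The section does not say what assessments follow.

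Sections 6.3 and 6.5 place two follow-up assessments at 1 and 4 months, counted from completion of the intervention. Table 3 shows Post at week 5 and follow-up at weeks 8 and 20. Sections 3.1 and 8.1 say, in general terms, that all subjects are followed.

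Section 8.3 limits the analysis to completers, with PI discretion to add a subject who completed most of the study.

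**The concern.** Stopping the stimulation and leaving the study are different events, and the plan gives no rule that keeps them apart. A subject who stops before the planned sessions are done has no defined start for the follow-up clock. A subject who is withdrawn has no further outcome visit at all.

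The introduction aims to tell responders from non-responders and to describe what is retained after 4 months without intervention. Subjects who stop after a complication, or who turn to other therapy during follow-up, are informative for both aims. If their visits are not made, those descriptions may rest on subjects who tolerated the intervention and stayed.

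This is a question of what is collected, and it comes before the question of who is analysed. The mixed models in section 8.2 use only what was recorded. The planned sensitivity imputation predicts from baseline data, which cannot carry the reason why someone stopped. The study is also unblinded (section 5.7), and the withdrawal decision rests partly on the PI's opinion.

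**Working it through.** There is no planned figure to reproduce: section 8.1 states that "no formal power calculations were performed for this study", and the documents give no expected withdrawal rate. The check is a reading of the passages together, followed by a count.

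**Reading**

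| Situation | Outcome visits afterwards | Adverse events afterwards |
|---|---|---|
| Completes the intervention | Week 5, then weeks 8 and 20 (6.3, 6.5, Table 3) | Asked about at each contact (9.8) |
| Stops early or is explanted early, not withdrawn | Not stated; the general statements in 3.1 and 8.1 apply, but the clock in 6.3 and 6.5 has no defined start | Asked about at each contact (9.8) |
| Withdraws or is withdrawn | None named (4.4.2) | Known events followed; related later events notified (9.5, 9.8, 9.17.4); no scheduled contact for new events |

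**Inputs for the count**

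- Arm size 4: "Four subjects will be assigned to each treatment arm based on availability" (5.2).
- One subject per AIS grade per arm (1.1). Check: 4 grades × 1 subject × 2 arms = 8, which matches section 8.1.
- Three post-intervention timepoints: weeks 5, 8 and 20 (Table 3).

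**One loss before week 5, no replacement**

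- Share of the arm: 1/4 = 25%. Share of the trial: 1/8 = 12.5%.
- Visits lost: 3 of 4 × 3 = 12 in the arm, and 3 of 8 × 3 = 24 overall.
- AIS grades still represented in that arm: 3 of 4.

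A withdrawal after week 5 but before week 8 loses 2 visits; one after week 8 loses 1.

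**Effect on a responder description.** Suppose every subject still observed responds. With m of 4 lost, completers show 100%, while the proportion among all 4 lies between (4 − m)/4 and 100%:

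- m = 1: between 75% and 100%.
- m = 2: between 50% and 100%.

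**How likely a loss is.** The withdrawal rate p per subject is an assumption, and subjects are taken as independent. P(at least one) = 1 − (1 − p)^n.

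| Assumed p | Arm of 4 | All 8 |
|---|---|---|
| 5% | 19% | 34% |
| 10% | 34% | 57% |
| 15% | 48% | 73% |
| 20% | 59% | 83% |
| 25% | 68% | 90% |

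For example, at 10%: 1 − 0.90^4 = 0.34 and 1 − 0.90^8 = 0.57.

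**The case against.** The best defence is that the plan is silent where it might seem to exclude. Section 4.4.2 applies to withdrawal from the study. Section 4.4.1 says that withdrawal leads to explantation, but nothing says that explantation leads to withdrawal. Twelve sessions is a goal in sections 6.2 and 6.4 (although Table 1 calls it a minimum), and sections 3.1 and 8.1 speak of following all subjects. A reader might infer that anyone who stops early loses the later visits by rule. The documents do not support that: for early stopping the loss is a risk left open by silence. For actual withdrawal, however, the gap in 4.4.2 stands.

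A reader might also infer that safety follow-up ends at withdrawal. It does not. Section 9.5 follows unresolved events and requires notification of deaths and possibly related events after participation ends. Sections 9.8 and 9.17.4 follow each event to resolution or stabilization. Section 4.4.1 provides for a contact attempt when a subject neither attends nor responds. Table 3 has no separate safety procedure at weeks 5, 8 or 20. What remains is narrower. Active questioning is tied to contacts and visits, and section 9.5 gives the instruction to report later events at the final scheduled visit. After an exit interview, no planned contact asks about new events.

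Section 10.1 invites a comparison, because for subjects who revoke authorization "attempts will be made to obtain permission to collect at least vital status at the end of their scheduled study period". That does not show that they are followed more closely than consenting withdrawn subjects, since it seeks a minimum of vital status and the latter keep the adverse event follow-up just described.

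Replacement is a fair point too. It can restore an arm to 4, but it does not supply the outcomes of the subject who left, and it is not offered after treatment-related adverse events.

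**Conclusion.** The point holds as a gap in outcome collection after withdrawal, and as a missing distinction between ending the intervention and ending participation. It should be corrected, but it does not undermine the pilot as a whole. One unreplaced loss before week 5 costs a quarter of an arm, that arm's only subject of one AIS grade and 3 of 12 post-intervention visits. It also widens a 100% completer response to a range of 75% to 100%. These counts rest on four subjects per arm and on the withdrawn subject attending no later visit. The probabilities of a loss rest on assumed rates of 5% to 25%.

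Two stronger readings go too far:

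- Loss is not confined to subjects in whom stimulation or the implant failed. Non-compliance and new information are listed reasons as well, and subjects may leave at any time. Selection by outcome is possible, not established.
- A zero-event upper limit could be quoted for late epidural safety: 1 − 0.05^(1/4) = 53% with 4 subjects followed, against 1 − 0.05^(1/3) = 63% with 3 (one-sided 95%). It assumes no events and no late information from the lost subject. The adverse event provisions contradict the second assumption. If that subject was explanted for infection, an implant event has already been seen.

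**What to change.** The change concerns data collection and analysis only, and leaves the decision on stimulation or explant as it is.

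1. In sections 4.4 and 5.3, state that ending stimulation or early explant, whenever it is decided, is not in itself withdrawal from the study.
2. Ask every consenting subject who stops early to attend the Post, 1-month and 4-month assessments already in Table 3 that need no implanted lead, counted from the last stimulation. Align sections 6.3 and 6.5 with this.
3. Treat the start of outside therapy as an event to record, with type and start date, and continue to assess the subject.
4. For subjects who decline visits but still consent to contact, ask about adverse events by telephone at the planned 1-month and 4-month dates.
5. Reserve the exit interview alone for subjects who refuse further contact.
6. Amend section 8.3 to include all treated subjects with available data, and flag observations made after outside therapy began. Without this step the added visits could go unanalysed.

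The cost is mainly protocol and consent wording. Some data after stopping will reflect outside therapy. A few more visits may be needed where a withdrawn subject is both followed and replaced; the documents do not show that these are budgeted, and section 8.1 says that budget, space and staff time set the sample size.
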